### ***Etiological diagnosis and group allocation***

Fulminant hepatitis A is defined by an acute onset of liver disease, due to HAV infection, with no known evidence of chronic liver disease, together with hepatic based coagulopathy (prothrombin time [PT]  $\geq 20$  seconds or international normalized ratio [INR]  $\geq 2.0$ ) that is not corrected by parenteral vitamin K and/or hepatic encephalopathy (must be present if the PT is 15–19.9 seconds or the INR is 1.5–1.9, but not if PT is  $\geq 20$  seconds or INR is  $\geq 2.0$ ) 5. After full investigations for possible etiologies, patients with proved etiology other than HAV or those with indeterminate FHF were not included.

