## **Material and methods**

### ***Study population:***

This study included 26 children with fulminant hepatitis A. They were recruited over a period of 4 years duration and divided into two groups. Group one is comprised of 18 children with fulminant HAV infection who received steroid therapy beside standard supportive measures (steroid group). The second group is comprised of 15 children with fulminant HAV infection who did not receive steroid therapy, but only standard supportive measures (non steroid group). All cases were recruited from the department of Pediatric Hepatology, Gastroenterology and Nutrition, National Liver Institute, Menofiya University. Those patients whose parents accepted to receive steroids were allocated in the steroids group; others were allocated in the control group. From each group a random sample was chosen using SPSS. An informed consent was signed by the parents of the steroid-treated patients before recruitment in the study which was approved by the Research Ethics Committee of National Liver Institute.

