### ***Treatment regimen and modifications***

Patients were initially assigned to receive prednisolone at a dose of 1 mg/kg/d or its equivalent dose of methylprednisolone (0.8 mg/kg/d) for those who cannot take oral prednisolone (as patients with encephalopathy or vomiting). In those with improved PT (while on steroid therapy) below 20 seconds in conscious patients or below 15 seconds in encephalopathic patients, the steroid dose was maintained for further two weeks then withdrawal started. In those who had deterioration of liver functions upon withdrawal, treatment was continued for a longer duration till satisfactory biochemical improvement was achieved. The treatment was scheduled to be discontinued if uncontrollable hyperglycemia, gastrointestinal bleeding, or brain edema develops.

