### ***Statistical analysis plan (SAP)***

Quantitative data were presented as mean  $\pm$  standard deviation (SD) while qualitative data were presented as number and percentage. For both homogenously distributed and non homogenously distributed quantitative data, significance was tested by either independent samples *t*-test or by Mann-Whitney U test, respectively. Chi-square test or Fisher's exact test was used for the measurement of the qualitative data significance. Significance was set at *P* value  $< 0.05$ . A stepwise regression analysis was performed to examine independent factors associated with the outcome. Standardized regression coefficient ( $\beta$ ), 95% confidence interval (CI) and *P* values of each independent factor are presented. Statistical analysis was performed using SPSS, version 13 (SPSS Inc, Chicago, IL, USA).

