## Results

**Table 1:** Outcome of steroid therapy

Characteristics	Steroid (n = 18)	Non-Steroid (n = 15)	P-value
Type of steroids			
Methylprednisolone	10 (55.6)	--	
Prednisolone	8 (44.4)	--	
Duration of steroids (days)			
Minimum-Maximum (median)	5 – 50 (22)	--	
Outcome			
Living	15 (83.3)	4 (26.7)	0.001
Dead	3 (16.7)	11 (73.3)	

[figure not shown]
Number of living patients were significantly higher in the steroid group compared to non-steroid group

**Table 2:** Stepwise regression analysis for parameters with significance between living and dead patients

Characteristics	$\beta$	P-value	95% CI	
			Lower	Upper
Steroid therapy	0.571	0.001	0.268	0.865
Prothrombin time (seconds)	NI	--	--	--

$\beta$ : regression coefficient; CI: confidence interval; NI: not included

Steroid therapy was the only independent parameter associated with survival of patients

**Figure 1.** Serial changes of prothrombin time (A) and total bilirubin (B) in the steroid group.

PT: prothrombin time

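### The survival effect called independent is the crude steroid comparison: prothrombin time, an incomplete severity measure under this entry rule, is not in the model, and entry encephalopathy is never compared between arms

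*Combined protocol and SAP*

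**What the plan says.** All section names refer to the combined protocol and SAP.

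- **Etiological diagnosis and group allocation.** Hepatic encephalopathy "must be present if the PT is 15–19.9 seconds or the INR is 1.5–1.9". It is not required once PT reaches 20 s or INR reaches 2.0. The section's other restriction concerns cause: "patients with proved etiology other than HAV or those with indeterminate FHF were not included". It defines no severity class for analysis.
- **Study population.** Allocation was not randomised: "Those patients whose parents accepted to receive steroids were allocated in the steroids group", and the remaining children were controls.
- **Treatment regimen and modifications.** The plan reads PT differently by consciousness; its response cut-offs are "below 20 seconds in conscious patients or below 15 seconds in encephalopathic patients". Methylprednisolone was "for those who cannot take oral prednisolone (as patients with encephalopathy or vomiting").
- **Statistical analysis plan.** "A stepwise regression analysis was performed to examine independent factors associated with the outcome". Candidate variables are not listed, and no comparison by encephalopathy is planned.
- **Results.** Table 1 gives survival by arm only: 15 of 18 with steroids and 4 of 15 without, P = 0.001. Table 2 is headed as covering parameters that differed significantly between living and dead children. It lists steroid therapy (β 0.571, P 0.001, 95% CI 0.268 to 0.865) and PT, which is marked as not included. The conclusion reads: "Steroid therapy was the only independent parameter associated with survival of patients".

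**The concern.** Parents chose the arm, so similar severity in the two arms cannot be presumed. The conclusion drawn from Table 2 invites the reader to think that severity has been dealt with. There are two reasons to doubt that.

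First, the entry rule leaves out conscious children whose PT and INR both lie in the lower band. The low-PT end of the cohort is therefore enriched for encephalopathy, and a lower PT need not mean milder disease when all children are pooled. The plan's own consciousness-specific PT cut-offs show that it does not treat PT alone as a sufficient yardstick.

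Second, even PT is absent from the final model. If encephalopathy was commoner among controls, part of the survival difference belongs to that imbalance and not to steroids. If it was commoner in the steroid arm, the crude figure understates the association. The documents do not show which applies.

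**Working it through.** **Inputs.** Table 1: 15/18 and 4/15 alive. Table 2: β 0.571, CI 0.268 to 0.865. The arms sum to 33, although the Study population section gives a total of 26; the figures below use 18 and 15, as in Table 1. Tests are taken as two-sided, which the SAP does not state.

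**1. Reproduce Table 1.** Pearson chi-square = 10.76, P = 0.00104, which agrees with the stated 0.001 (Fisher's exact P = 0.0016).

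**2. Reproduce Table 2 from steroid use alone.**
- Risk difference = 15/18 − 4/15 = 0.833 − 0.267 = 0.567.
- Residual sum of squares = 15×3/18 + 4×11/15 = 5.433; divided by 31 df = 0.1753.
- Standard error = √[0.1753 × (1/18 + 1/15)] = 0.1464.
- 95% CI = 0.567 ± 2.040 × 0.1464 = 0.268 to 0.865; P = 0.0005.
- Standardized β = phi = (15×11 − 3×4)/√(18×15×19×14) = 0.571.

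Both printed figures are matched to three decimals with no other variable in the model. Table 2 sets the standardized coefficient beside the interval of the unstandardized risk difference, and neither is adjusted for severity.

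**3. What the missing split could do.** The documents give no encephalopathy counts, so the splits below are assumptions; each adds up to the Table 1 margins. Per stratum, with a steroid survivors, n₁ steroid and n₀ control children, m survivors and N children in all: E = n₁m/N and V = n₁n₀m(N−m)/[N²(N−1)]. Mantel-Haenszel z = Σ(a−E)/√ΣV.

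| Encephalopathic alive (steroid v control) | Conscious alive (steroid v control) | Encephalopathic share | Σ(a−E)/√ΣV | z | P |
|---|---|---|---|---|---|
| 0/2 v 0/10 | 15/16 v 4/5 | 11% v 67% | 0.524/√0.345 | 0.89 | 0.37 |
| 1/3 v 1/11 | 14/15 v 3/4 | 17% v 73% | 1.150/√0.625 | 1.46 | 0.15 |
| 5/7 v 1/10 | 10/11 v 3/5 | 39% v 67% | 3.592/√1.558 | 2.88 | 0.004 |
| 7/10 v 2/9 | 8/8 v 2/6 | 56% v 60% | 4.549/√2.000 | 3.22 | 0.001 |

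Over every arithmetically possible split, z runs from −0.99 to 4.28. The lower end needs near-complete separation, for example all 15 controls but only 3 of 18 steroid children encephalopathic. When the shares differ by less than 5 percentage points, z is 3.13 to 3.85.

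**4. Imbalance needed to explain everything.** Assume no steroid effect, with survival of 10% if encephalopathic and 90% if conscious. The share needed is (0.90 − observed survival)/(0.90 − 0.10): (0.90 − 0.833)/0.80 = 8% in the steroid arm and (0.90 − 0.267)/0.80 = 79% among controls.

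**5. Precision after stratifying.** At the observed survival rates, Fisher's exact test has about 92% power overall and about 63% in a stratum of 9 v 8.

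**The case against.** The strongest reply is that the entry rule does less harm than it first appears.

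- *PT cannot rank severity.* A reader might infer this, but the documents do not support it. PT still orders children of the same consciousness level, and the heading of Table 2 implies that PT did separate living from dead. Under assumed PT distributions (median 22 to 28 s, log-SD 0.45), only about 4–11% of eligible children fall below 20 s, and any reversal of the PT gradient is confined to that band.
- *Every child at PT 15–19.9 s is encephalopathic.* This also goes too far. The criterion is PT or INR, so a conscious child with PT below 20 s may qualify with INR of 2.0 or more; the text does not settle how the two clauses interact.
- *The entry rule creates the bias.* Any bias here is ordinary confounding by encephalopathy under parental choice, which could arise under any entry rule.
- *Encephalopathy was ignored.* It may have been screened and dropped as non-significant; the documents do not say. Non-significance in 33 children would not show that the arms were balanced.
- *Ten of 18 on methylprednisolone shows severity.* It does not, because vomiting was also a reason for that form, and controls have no counterpart.

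These replies narrow the point. They do not answer the fact that the effect called independent is unadjusted and that encephalopathy by arm is not shown.

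**Conclusion.** The point stands in limited form. Table 2 is exactly the crude comparison, so the documents support an association in a non-randomised, unadjusted comparison and not an independent effect. That conclusion rests on the printed figures alone.

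The entry rule adds that PT by itself would be only a partial remedy, since its meaning depends on consciousness. The direction and size of any bias are unknown. The stratified results rest on assumed splits and run from no clear difference to a strong one.

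A reader might infer that the survival result is wrong. The documents do not show that: with similar encephalopathy shares the association stays strong (z above 3), and explaining it away entirely takes a very large imbalance, such as 8% v 79%.

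**What to change.** 1. Classify each child at entry as conscious or encephalopathic from the records behind the entry definition. The information should exist for children below the PT/INR threshold, who could not qualify without it. Confirm that it is available for controls with PT of 20 s or more, for whom eligibility did not depend on it.
2. Report encephalopathy, PT and INR at entry by arm.
3. Show survival by arm within each class. Beside the crude result, add an exact stratified comparison with a common odds ratio and its interval.
4. Use PT as a severity covariate only together with that class.
5. Replace *independent* with wording such as *associated in an unadjusted, non-randomised comparison*, or *adjusted for entry encephalopathy* once that analysis is done. Adjusting for one factor would still not remove other effects of parental choice.

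The cost is one extra table and probably no new data collection. The interval will be wider in 33 children, and the strata will be thin enough that they should be read mainly as description.

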### ***Serum viral markers***

Anti-HAV IgM was detected by enzyme linked immunosorbent assay (ELISA) (Dia Pro, Italy). Anti-hepatitis E virus IgM was tested by ELISA (Dia Pro, Italy). Hepatitis B surface antigen (HBsAg), anti-hepatitis B core IgM and IgG types, were tested for by ELISA kits (Sorin Biomedica Co, Spain). HBV-DNA was tested by COBAS AMPLICOR monitor test, version 2.0, Roche Molecular Systems, Inc., Branchburg, NJ, 08876 USA. Hepatitis C virus (HCV) antibody was tested by 4th generation ELISA (Innogenetics, Ghent-Belgium). Real-time polymerase chain reaction for HCV-RNA was performed using COBAS® Ampliprep/COBAS® TaqMan®, Roche Molecular Systems, Inc., Branchburg, NJ, 08876 USA.

### ***Treatment regimen and modifications***

Patients were initially assigned to receive prednisolone at a dose of 1 mg/kg/d or its equivalent dose of methylprednisolone (0.8 mg/kg/d) for those who cannot take oral prednisolone (as patients with encephalopathy or vomiting). In those with improved PT (while on steroid therapy) below 20 seconds in conscious patients or below 15 seconds in encephalopathic patients, the steroid dose was maintained for further two weeks then withdrawal started. In those who had deterioration of liver functions upon withdrawal, treatment was continued for a longer duration till satisfactory biochemical improvement was achieved. The treatment was scheduled to be discontinued if uncontrollable hyperglycemia, gastrointestinal bleeding, or brain edema develops.

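### Conditions that stop steroids are not entry exclusions, and allocation is not randomised, so children with one at presentation could have been steered to the non-steroid group

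*Combined protocol and SAP*

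**What the plan says.** - **Stopping steroids** (Treatment regimen and modifications): "The treatment was scheduled to be discontinued if uncontrollable hyperglycemia, gastrointestinal bleeding, or brain edema develops". The sentence concerns conditions that arise on treatment. No rule is given for a child who has one before the first dose.
- **Entry** (Etiological diagnosis and group allocation): the case definition requires coagulopathy and/or encephalopathy, "with no known evidence of chronic liver disease". The only further exclusion is by cause: "patients with proved etiology other than HAV or those with indeterminate FHF were not included". Brain edema, gastrointestinal bleeding and uncontrollable hyperglycemia are not mentioned.
- **Allocation** (Study population): "Those patients whose parents accepted to receive steroids were allocated in the steroids group; others were allocated in the control group". Then: "From each group a random sample was chosen using SPSS". The same section also describes the groups by what was received: "Group one is comprised of 18 children with fulminant HAV infection who received steroid therapy", and a second group of 15 who did not receive it. Signed consent is reported only for parents of steroid-treated children.
- **Result** (Results): Table 1 gives 15 of 18 alive v 4 of 15, P = 0.001. Table 2 keeps steroid therapy (β = 0.571, 95% CI 0.268 to 0.865) and lists prothrombin time as not included. The text then names steroids as the sole independent factor for survival.

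**The concern.** The plan treats three conditions as incompatible with continuing steroids but does not apply them at entry. A child who presents with brain edema or active bleeding meets every entry criterion, yet a clinician or parent might well hold back from starting steroids. If that happened, the child received supportive care only and fits the description of the second group.

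The survival comparison would then set children who could be given steroids against a group that also holds children who could not. If such children have a worse prognosis, the difference is biased in favour of steroids. Adjusting for parental preference would not remove this bias, because these controls might have no counterpart in the steroid group. At stake is the claim that steroid therapy is independently associated with survival.

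**Working it through.** **Inputs.** Table 1: steroid 15 alive, 3 dead (n = 18); non-steroid 4 alive, 11 dead (n = 15). Significance level 0.05 from the SAP, taken as two-sided because sidedness is not stated. Study population opens with a total of 26, but its group sizes give 18 + 15 = 33; Table 1 uses 33, and so does this check.

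**Step 1: reproduce the printed P.** Pearson chi-square without correction is n(ad − bc)² / (product of the four margins) = 33 × (15×11 − 3×4)² / (18×15×19×14) = 33 × 153² / 71,820 = 10.756, so P = 0.00104. This rounds to the printed 0.001. Fisher's exact test, which the SAP also allows, gives 0.0016.

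**Step 2: does Table 2 adjust for anything?**
- Standardised coefficient with one binary predictor = phi = 153/√71,820 = 0.571, the printed β.
- Unstandardised least-squares slope = 15/18 − 4/15 = 0.567. Its 95% CI is 0.268 to 0.865, the printed interval.

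The model is the Table 1 comparison in another form. It controls for no baseline condition.

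**Step 3: remove k affected control deaths.** The documents give no count, so k is an assumption. The table becomes 15/18 v 4/(15 − k) alive.

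| k | Control alive | Difference (points) | Fisher P | Uncorrected chi-square P |
|---|---|---|---|---|
| 0 | 4/15 | 56.7 | 0.0016 | 0.0010 |
| 3 | 4/12 | 50.0 | 0.0086 | 0.0054 |
| 4 | 4/11 | 47.0 | 0.017 | 0.0098 |
| 5 | 4/10 | 43.3 | 0.035 | 0.019 |
| 6 | 4/9 | 38.9 | 0.072 | 0.037 |
| 7 | 4/8 | 33.3 | 0.149 | 0.077 |
| 8 | 4/7 | 26.2 | 0.30 | 0.17 |

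Fisher's test passes 0.05 at k = 6 (6/11 = 55% of control deaths). The uncorrected chi-square passes it at k = 7 (7/11 = 64%).

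**Step 4: apply the restriction to both groups.** A common entry rule would also remove affected steroid-group children.
- 6 control deaths and 1 steroid death removed: 15/17 v 4/9, difference 88.2 − 44.4 = 43.8 points, Fisher P = 0.028.
- 7 control deaths and 2 steroid deaths removed: 15/16 v 4/8, difference 93.8 − 50.0 = 43.8 points, Fisher P = 0.028.

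Step 3 alone is therefore one-sided. The restricted result depends on how many children are affected in each group, and the documents give neither number.

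**The case against.** The strongest reply is that the only written allocation rule is parental acceptance. Read in full, the sentence containing "others were allocated in the control group" refers to children whose parents did not accept steroids, not to children judged clinically unsuitable. On that wording, a child with brain edema and accepting parents goes to the steroid group. The stopping sentence covers later events and is not an entry bar. Severe presentation did not in itself bar steroids: methylprednisolone was provided for children who could not take the oral drug because of encephalopathy or vomiting, and 10 of the 18 received it.

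This part stands. A reader might infer that affected children were in fact placed in the control group and make up some of its deaths. The documents do not support that. They report no child refused steroids and no count of the conditions at entry in either group.

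The reply does not close the gap, however. The groups are also described by receipt of steroids, and the consent statement does not show that every control was offered them. Encephalopathy leads only to a change of formulation, whereas brain edema is a reason to stop. The shortest steroid course in Table 1 is 5 days. That would fit a steroid group with no child who had a stopping condition at the start, but it proves nothing: there may have been none in either group, the random sampling may have dropped them, or the rule may not have been applied to them.

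Two further objections hold. The problem is one branch of the wider weakness of non-random allocation, so baseline severity reporting would cover part of it. Part of the document was also not available for this review, so a baseline table there cannot be ruled out.

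**Conclusion.** The concern holds as a possibility that the available text leaves uncontrolled, not as a demonstrated bias. The three conditions are reasons to stop steroids but not entry exclusions, allocation is not randomised, and the Table 2 model is the crude comparison. The likely direction favours steroids, on the assumption that affected children were steered away from steroids and had a worse prognosis.

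The size cannot be fixed. Removing control deaths only, Fisher's P stays below 0.05 for 1 to 5 of the 11, although the difference falls from 56.7 to 43.3 points at 5. At 6 it is 0.072. Removing affected steroid-group deaths as well can bring it back below 0.05. It would be wrong to conclude that the survival difference is explained by this route: more than half of the control deaths would have to be affected, with none removed from the steroid group, before significance is lost on Fisher's test. This is a cheap and worthwhile improvement, not a condition on which the study stands or falls.

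**What to change.** 1. State how children who had one of the three conditions at presentation were handled.
2. From the charts, record for all 33 children whether each condition was present at entry, and tabulate by group.
3. Repeat Tables 1 and 2 in children free of all three at entry, applying the same rule to both groups. Keep children who developed a condition later in their original group.
4. Show the restricted result beside the all-children comparison, with the number removed from each group. If the two differ, limit the statement that steroids are the sole independent factor for survival.

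The cost is a chart review of 33 children for three conditions and one re-run of two tables. The downside is a smaller comparison set and probably a less favourable difference. The change concerns only who is compared; no treatment or stopping rule is altered.

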### ***Outcome assessment***

The parameters of the primary response were improvement of PT followed by improvement of alanine transaminase and aspartate transaminase together with decreasing bilirubin during the period of observation. The overall clinical outcome (recovery or death) was

considered secondary response parameter. Treatment tolerability and side effects were also monitored.

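### The primary laboratory response has no common assessment day, combining rule or handling of death, and both inferential statements in the available text rest on survival, the secondary outcome

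*Combined protocol and SAP*

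**What the plan says.** Under Outcome assessment the primary outcome is a laboratory response: "The parameters of the primary response were improvement of PT followed by improvement of alanine transaminase and aspartate transaminase together with decreasing bilirubin". Its only time reference is in the phrase "together with decreasing bilirubin during the period of observation". Recovery or death is "considered secondary response parameter".

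Two other sections give PT figures. Etiological diagnosis and group allocation sets entry limits for all children: PT of at least 20 s or INR of at least 2.0, with encephalopathy needed at lower values (it "must be present if the PT is 15–19.9 seconds or the INR is 1.5–1.9"). Treatment regimen and modifications uses matching PT values as a condition for what happens next to steroid treatment: "In those with improved PT (while on steroid therapy) below 20 seconds in conscious patients or below 15 seconds in encephalopathic patients".

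For quantitative data the SAP says that "significance was tested by either independent samples" t-test or Mann-Whitney U test. Qualitative data get chi-square or Fisher's exact test. A stepwise regression is run on an outcome that the SAP does not name.

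The Results make two inferential statements. Under Table 1: "Number of living patients were significantly higher in the steroid group compared to non-steroid group". Under Table 2: "Steroid therapy was the only independent parameter associated with survival of patients". The caption of Figure 1 covers serial PT and total bilirubin in the steroid group only.

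**The concern.** A primary outcome that is to be compared between arms needs a time, a definition of response and a rule for children who die before the time of assessment. Here 14 of 33 children died, and very unevenly by arm. Without a death rule the primary analysis is not one analysis but several, and they can disagree.

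The inference that is reported concerns the outcome ranked second. It appears twice, the second time in language that suggests adjustment for other factors. A reader could take this as a positive primary result supported by an independent multivariable confirmation. The available text offers neither.

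**Working it through.** **Is the definition complete?**

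- Assessment day: none in Outcome assessment or the SAP, and the length of observation is not stated.
- Size of change: none in Outcome assessment. The PT cut-offs under Treatment regimen and modifications (below 20 s if conscious, below 15 s if encephalopathic) are tied to continuing steroids. They are not linked to the primary response or extended to controls. They have no counterpart for INR, on which a child may enter, nor for ALT, AST or bilirubin.
- Combining rule for PT, ALT, AST and bilirubin: none.
- Death: no rule in either section.

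**Reproducing the reported figures.** Inputs are the Table 1 counts: steroid 15 living, 3 dead; non-steroid 4 living, 11 dead.

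- Correlation of arm with survival: phi = (15×11 − 3×4)/√(18×15×19×14) = 153/√71,820 = 0.571.
- Uncorrected chi-square = 33 × phi² = 10.76, P = 0.00104. This matches the printed 0.001. Fisher's exact test, two-sided, gives 0.0016.
- Least-squares slope of survival (1/0) on arm (1/0): 15/18 − 4/15 = 0.567.
- Residual sum of squares: 18×(15/18)(3/18) + 15×(4/15)(11/15) = 2.500 + 2.933 = 5.433 on 31 degrees of freedom, so the variance is 0.1753.
- Standard error: √[0.1753 × (1/18 + 1/15)] = 0.146. With t = 2.04, the 95% CI is 0.268 to 0.865, P = 0.0005.

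Table 2 prints 0.571, 0.268 to 0.865 and P = 0.001. The Table 1 counts alone therefore give both the coefficient and the interval. PT is marked as not included, so the final model holds nothing but arm. The printed coefficient is the standardized one, while the interval belongs to the unstandardized slope (midpoint 0.5665); this does not alter the point.

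**What the death rule can do.** After all deaths, laboratory values can exist for at most 15 − 11 = 4 control and 18 − 3 = 15 steroid children. As an illustration, assume that every survivor improves and that assessment falls after all deaths:

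| Rule for deaths | Steroid | Non-steroid | Fisher P |
|---|---|---|---|
| Counted as non-response | 15/18 | 4/15 | 0.0016 |
| Excluded | 15/15 | 4/4 | 1.0, by construction |

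Under the first rule the uncorrected chi-square P is 0.001. If improvement before death counted as response, the answer would depend on data that are not reported.

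**How much a worst-rank analysis would reflect mortality.** Under the same timing there are 18×15 = 270 between-arm pairs. Steroid survivor against control death: 15×11 = 165. Steroid death against control survivor: 3×4 = 12. Death against death (tied): 3×11 = 33. Survivor against survivor: 15×4 = 60. Laboratory values decide only 60 of the 270 pairs (22%).

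**The case against.** The best defence is that the laboratory response was never meant as a between-arm endpoint. The protocol speaks of response, attaches PT values to improvement during steroid therapy, and captions Figure 1 for the steroid group alone. On that reading the laboratory outcome describes treated children, survival is the only between-arm outcome, and a clarification of wording would be enough. This reading is plausible and the documents do not rule it out. It does not remove the point: a description without a comparator cannot separate a steroid effect from natural recovery, and survival is still ranked secondary.

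It is also fair to say that PT is not without any threshold, since the treatment section gives numbers. The gap is that they are not declared as the endpoint for both arms. The illustration rests on an assumption about survivors, and the 15/15 v 4/4 result follows from that assumption. It shows that the rule matters and does not estimate what the data would show.

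Three stronger inferences are tempting and are not supported:

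- That control laboratory results were left out. Some pages between the SAP and the Results, and Figure 1 itself, could not be seen, so absence is not established.
- That a survivors-only comparison is biased by a known amount or in a known direction. Death dates and laboratory values by arm are not given.
- That the survival difference is miscalculated. The counts reproduce the printed results, and Table 2 does add that PT was considered and not retained.

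**Conclusion.** The point holds in limited form. As a between-arm endpoint, the primary response lacks a day, a combining rule and a death rule, and its only PT cut-offs sit in a steroid-continuation rule. With 11/15 v 3/18 deaths, the stated t-test or Mann-Whitney test applied after the deaths would compare at most 4 with 15 selected survivors. Under the stated assumptions, the choice of death rule alone moves the result from P = 0.0016 to no difference.

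In the available text the between-arm evidence is one unadjusted comparison of the secondary outcome, presented twice. That conclusion rests on the printed counts and needs no assumption. What should change is how the result is labelled and read; the survival counts stand. The plan should be corrected on this point. Allocation by parental acceptance and the mismatch between 26 children and 18 + 15 = 33 are separate matters to be raised on their own.

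**What to change.** 1. State whether the laboratory response is a between-arm endpoint or a within-arm description of treated children. If it is a description, draw no steroid effect from Figure 1.
2. If it is between-arm:
   - Define one PT/INR response for both arms, as an analysis endpoint only and not a treatment rule. Fix encephalopathy status at baseline. Otherwise a child who enters encephalopathic at PT 17 s and regains consciousness at PT 17 s would count as a responder with no laboratory change. Say how children who entered on INR alone are counted.
   - Compare all children at one day counted from eligibility. Disclose that the day was chosen post hoc, and show a second day.
   - Count death as non-response (Fisher) or rank it worst (Mann-Whitney). Both tests are already in the SAP.
   - State that the result is driven largely by mortality, and give survivors' laboratory values by arm descriptively.
3. Label the survival comparison and Table 2 as secondary-outcome analyses that are the same unadjusted comparison. Alternatively, disclose a post hoc change to survival as primary and give the day on which status was assessed.

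The cost is rewording of the SAP and Results and, if step 2 applies, re-analysis of existing records. The downside is a less favourable label for the survival result and a composite that mostly re-expresses mortality.
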